Potential risks to patient participants are considered minimal. For patients in all study arms, there is a potential breach of privacy of individually identifying study data. To minimize this risk, no individually identifying patient information will be made available in publication or dissemination efforts. Results that are shared will be in aggregate form.

For patients whose providers are exposed to the CDS, there are several additional potential risks. First, the CDS may not display all relevant clinical information about the patient, as the CDS is limited to what is contained in the EHR. Second, it is possible that the CDS could erroneously attribute a condition or drug to a patient based on the EHR. In the design phase, the study team will seek and feedback from multiple sources to ensure that the content and CDS firing is as accurate and appropriate as possible. Before implementation, several investigators will review and test the CDS firing to optimize the information displayed. Provider training will inform providers of these limitations and offer strategies to further minimize these risks. Throughout the implementation phase, the study team will request feedback from providers using the CDS to identify any issues and modify the CDS, if needed.

Third, the CDS may be inappropriate for a given individual patient and, if applied without further checking the clinical status of a given patient, could lead to erroneous therapy, adverse events, disability, or death. However, the clinical recommendations are personalized based on the patient's medical problem list, allergies and current medications. The risk of untoward consequences from such clinical actions is considered minimal. Moreover, this potential risk is routinely present in every clinical encounter in the health care system. Fourth, the potential shift in provider prescribing and/or pain management recommendations may also have unintended consequences on patients' post-procedure pain management. It is possible that this shift could cause under-controlled pain. Providers encounter this in current dental practice and will address it in a similar fashion consistent with the reasonable standard of care.

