6 STUDY INTERVENTION

6.1 STUDY INTERVENTION(S) ADMINISTRATION

6.1.1 STUDY INTERVENTION DESCRIPTION

The study intervention will be active within HealthPartners Dental Group for 12 months or until patient accrual goals are met. After completion of the study, the HealthPartners Dental Group will decide whether to continue its activity, but this will be beyond the study's scope.

Standard Practice: Providers will not receive point of care decision support, serving as the control group representing usual care. Patients will receive usual dental care.

CDS: Providers will receive point of care decision support to guide pain management recommendations and prescribing for patients who receive dental extractions. The clinical decision support will highlight: (1) potential medication interactions between the patient's current medications and commonly recommended analgesics for patients following dental extractions; (2) relevant health conditions that may impact pain management strategies; and (3) automated access to the Prescription Drug Monitoring Program. Patients will receive usual dental care [when implemented by HealthPartners Dental Group: access to the Prescription Drug Monitoring Program via the clinical decision support tool will be suspended to align with the organization approach via the electronic health record].

CDS-E: Providers will receive point of care decision support to guide pain management recommendations and prescribing related to dental extractions. The clinical decision support will highlight: (1) potential medication interactions between the patient's current medications and commonly recommended analgesics for patients following dental extractions; (2) relevant health conditions that may impact pain management strategies; and (3) automated access to the Prescription Drug Monitoring Program [when implemented by HealthPartners Dental Group: access to the Prescription Drug Monitoring Program via the clinical decision support tool will be suspended to align with the organization approach via the electronic health record].

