In addition, patients will receive an educational handout prior to the extraction procedure comparing effectiveness for managing pain, risks and benefits of non-opioid pain medications and opioid medications. This handout intends to initiate a conversation between the patient and provider about patient needs, goals and preferences. The patient will also receive an education handout about pain management after dental extraction for their reference. This handout intends to normalize the experience of some discomfort and to help patients decide about whether to contact their provider for additional help to manage their pain after extraction. Patients will receive usual dental care.

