7 STUDY INTERVENTION DISCONTINUATION AND PARTICIPANT DISCONTINUATION/WITHDRAWAL

7.1 DISCONTINUATION OF STUDY INTERVENTION

Providers should exercise clinical judgment and can at their discretion disregard any information the CDS offers. As such, patients will receive usual dental care, regardless of study arm.

Hospitalizations documented within the HealthPartners electronic health record that occur within a 72-hour window following the index extraction encounter will be chart reviewed for severity and relatedness on a quarterly basis during the intervention period by Co-investigator and/or PI [name]. These hospitalizations rates will be compared at a frequency determined by the DSMB or quarterly whichever is greater.

Based on the relevant data, the study team in consultation with the DSMB would determine whether the study intervention needed to be modified or discontinued.

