8.3.3.3 EXPECTEDNESS

Adverse events will be considered unexpected if the nature, severity, or frequency of the event is not consistent with the risk information previously described for the intervention. As the intervention for this study is a pain management clinical decision support module, inadequately managed pain, drug interactions or side effects related to pain medications are expected adverse events.

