9.4.3 ANALYSIS OF THE SECONDARY ENDPOINT(S)

H2: Providers in the CDS and CDS-E strategy arms will increase their likelihood of satisfying the composite endpoint defined by: 1) prescribing or recommending non-opioid analgesics at the extraction encounter and 2) not prescribing opioids at the index encounter for patients following extractions more than providers in the SP arm.

Analysis plan: Hypothesis H2 posits that patient encounters at which extractions are performed by dental providers in the CDS and CDS-E arms will have a larger increase in the likelihood of receiving a prescription or recommendation for non-opioid analgesics and not prescribing opioids at the index encounter than patient encounters in the SP arm when comparing independent samples of patient encounters before the implementation to patient encounters following the implementation. The same analytic strategy used for the primary endpoint will be used for this secondary endpoint and will be conducted on the Intention to Treat Analysis Dataset.

H3 (alternative): Patients will report higher levels of the extent of shared decision making in the CDS-E arm than the CDS or SP arms.

Analysis plan: Hypothesis H3 posits that patients will report higher levels of the extent of shared decision making in the CDS-e arm than CDS or SP arms during the strategies implementation time period. A general linear mixed-model regression with an identity link and normal error distribution will be used to test the effects of the implementation strategies. The patient-level endpoint is the score on the 3-item composite of adapted Collaborate Shared Decision Making, and is considered an interval-level variable. This endpoint will be predicted by 2 fixed-effects terms for study arm of CDS (CDS vs. SP) and CDS-E (CDS-E vs. SP). A random intercept for provider will be included in the model. Additional covariates to be included will be described in the MOP. Model-predicted means and confidence intervals for the endpoint will be summarized by study arm. A contrast will estimate the difference in the mean of the endpoint for patients in the CDS-e arm vs. CDS and SP (pooled). This analysis will be conducted on the Intention to Treat Analysis Dataset.

H4 (descriptive): Compare patient report of mean pain in the week following tooth extraction across the 3 study arms.

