9.4.4 SAFETY ANALYSES

The study does not include objectives or formal endpoints concerning safety. However, potential harm monitoring activities will be conducted as described in section 8.2, and analysis activities conducted as described below.

Identify whether the CDS inappropriately fires or inappropriately offers considerations

The frequency of notifications and content areas (usability, potential safety, or other) will be summarized by study arm (CDE or CDS-E) and provider type.

Identify potential adverse events

Frequencies, proportions and 95% confidence intervals on proportions of patients having hospitalizations documented in the HealthPartners electronic health record within 72-hours of the extraction encounter deemed as adverse events will be summarized by study arm. The

patient encounter study population for H1 and H2 for patients seen following the implementation of the interventions will be used for this analysis. Events with non-overlapping confidence intervals on the proportions by study arm will prompt the study team to assess diagnostic codes related to the encounters from the electronic health record. Frequencies and proportions of diagnostic codes by study arm will be computed.

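### Section 9.4.4 compares hospitalizations between arms only by whether confidence intervals overlap; adding difference estimates with 95% CIs would be a cheap improvement

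*Combined protocol and SAP*

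**What the plan says.** Section 9.4.4 states that there are no safety objectives or formal safety endpoints. It then plans "Frequencies, proportions and 95% confidence intervals on proportions of patients having hospitalizations documented in the HealthPartners electronic health record within 72-hours" of the extraction, limited to those deemed adverse events and shown by study arm. The between-arm rule is: "Events with non-overlapping confidence intervals on the proportions by study arm will prompt the study team to assess diagnostic codes". What follows a prompt is a table of diagnostic codes, again by arm. The section does not name the interval method or say whether the intervals allow for clustering by provider.

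Section 7.1 has these hospitalizations chart-reviewed each quarter for severity and relatedness, and adds: "These hospitalizations rates will be compared at a frequency determined by the DSMB or quarterly whichever is greater". It gives no estimator.

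On the source of risk, section 2.3.1 says: "For patients whose providers are exposed to the CDS, there are several additional potential risks". Section 6.1.1 gives CDS and CDS-E the same decision support; CDS-E adds patient handouts. Of the post-extraction handout it says: "This handout intends to normalize the experience of some discomfort and to help patients decide about whether to contact their provider". The primary contrasts in section 9.4.2 are pairwise: CDS against SP and CDS-E against SP.

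**The concern.** Someone asking how much the decision support could raise hospitalizations will find three separate proportions and a note on whether their intervals overlap. Nothing in the supplied text gives a difference between arms, whether pairwise or combined. A crude difference can be worked out from the by-arm counts. An interval that allows for provider clustering cannot, and providers are the randomized unit.

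The overlap rule is also strict unless clustering is strong and ignored. With few events, real harm could pass without a prompt. The practical stake is modest: the effect estimate is the main gain, and the prompting is secondary.

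**Working it through.** **Inputs.** Section 9.2 expects 6,900 intervention-period patients of 51 providers, and section 6.3 allocates 1:1:1. That gives 17 providers and 6,900/3 = 2,300 patients per arm, about 135 per provider. The plan states no safety figure to reproduce. As a check on this layout, the 80% power for H1 reproduces: 2,300/[1 + 134.3 × 0.3] = 55.7 effective patients per arm, and 38% against 15% at two-sided 0.05 gives 79.4%. Hospitalization rates and safety ICCs below are assumptions.

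**Strictness of the overlap rule.** If each arm's proportion has standard error s, two 95% CIs separate when the difference exceeds 2 × 1.96 × s. The difference has standard error s√2. The threshold is therefore 2 × 1.96/√2 = 2.77 standard errors, or p = 0.0056.

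**Precision of a difference.** Under no effect, the combined line has a standard error √[(1/2,300 + 1/4,600)/(2/2,300)] = 0.866 of a one-arm difference, about 13% smaller. At a 0.5% rate the one-arm half-width is 1.96 × √(0.005 × 0.995 × 2/2,300) = 0.41 points, against 0.35 combined. At design effect 1.5 these become 0.50 and 0.43. At ICC 0.01 (design effect 1 + 134 × 0.01 = 2.34) they become 0.62 and 0.54. A doubling is a rise of 0.5 points. With an observed difference of zero, both lines exclude it without clustering, and neither does at ICC 0.01.

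**Prompting, no clustering.** This is exact enumeration over three binomial counts with n = 2,300 each. The plan's rule is taken as an active arm's Clopper-Pearson lower limit above SP's upper limit. The added rule is a Newcombe 95% lower limit above zero on any of the three difference lines. Each cell shows the plan, then the plan with the three lines.

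| SP rate | No effect (false upward) | Both active arms double | One active arm doubles |
|---|---|---|---|
| 0.05% | 0.00% → 0.42% | 0% → 6% | 0% → 3% |
| 0.1% | 0.01% → 2.07% | 1% → 18% | 1% → 11% |
| 0.25% | 0.16% → 3.55% | 8% → 39% | 5% → 26% |
| 0.5% | 0.26% → 3.96% | 26% → 68% | 16% → 50% |
| 1% | 0.34% → 4.43% | 64% → 92% | 47% → 80% |

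**Where the gain comes from, at 0.5%.** The two pairwise lines alone prompt in 66.3% (both double) and 49.5% (one doubles), with 3.8% false. The plan plus only the combined line gives 58.5% and 22.5%, with 1.9% false. At similar false-prompt rates and harm in both arms, pairwise 97.5% CIs flag 52.3% (1.7% false) and the combined 95% CI flags 58.4% (1.9% false). Combining arms is thus worth about 6 points. The rest comes from using an interval for the difference.

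**With clustering, at 0.5%, both arms doubling.** This is 60,000 beta-binomial simulations, 17 providers of 135 patients per arm, with counts and sizes for the added lines divided by the true design effect.

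- Design effect 1.5: 14% → 51% if the by-arm CIs allow for clustering, 33% → 51% if they do not.
- ICC 0.01: 6% → 35% if they do, 40% → 40% if they do not. In the second case the overlap rule is no longer strict, because 2.77/√2.34 = 1.81 true standard errors.

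**The case against.** The strongest case against is that little depends on this. There is no formal safety endpoint, a prompt only produces a code tabulation, section 7.1 already has the hospitalizations chart-reviewed quarterly, and the DSMB reviews safety by arm (section 10.1.6). That stands, and it keeps the point optional. The Data Safety Monitoring Plan, DSMB charter and Manual of Procedures were not supplied and may specify a method for the comparison in 7.1. That also stands, so the claim covers only the text available.

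A reader might infer that the real gap is a missing pooled estimate of the tool both active arms share, with H3 as precedent for pooling. The documents do not support this. The contrast that isolates the tool is CDS minus SP, because CDS has no handouts. The H3 contrast pools CDS with SP against CDS-E, so it treats the active arms as different. The combined line estimates the tool effect only if the handouts do not change hospitalization, and 6.1.1 intends one of them to influence whether patients contact their provider. It also dilutes harm confined to one arm: at 0.5%, with one arm doubling, it flags 19.6%, against 49.3% for that arm's own difference.

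The prompting gains are also driven by assumptions. That is true, and at ICC 0.01 with unadjusted by-arm CIs there is none. The case for an effect estimate with an interval does not depend on them.

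**Conclusion.** This holds as a cheap improvement. Section 9.4.4 is not wrong: by-arm reporting is legitimate, and the overlap rule is a trigger, not a test. A reader might infer that the plan leaves patients unmonitored or would hide harm. The chart review and DSMB oversight argue against that, and without a documented event rate the size of any missed signal is unknown.

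The supportable conclusion is that the only stated between-arm rule gives no effect size and, unless clustering is substantial and ignored, needs about 2.77 standard errors. Difference intervals correct both at almost no cost. The pairwise differences carry most of the value, and the combined line adds some precision under a stated proviso. The absence of the differences and the arithmetic are firm; the prompting figures are conditional on assumed rates and ICCs.

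**What to change.** Keep the by-arm table and its trigger, and add to 9.4.4, for the final analysis only:

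*The proportion of patients with a 72-hour hospitalization deemed an adverse event will also be reported as the differences CDS minus SP and CDS-E minus SP and, as a supplementary line, CDS and CDS-E combined minus SP. Each will have a 95% Newcombe interval, with counts and sample sizes divided by the estimated design effect for provider clustering (not below 1). A lower limit above zero on any line will also prompt the diagnostic-code tabulation.*

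It would help to state as well whether the by-arm intervals allow for clustering.

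The cost is three lines in one table and no new data. There are three downsides:

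- False upward prompts at a single look rise from 0.3% to about 4% at an assumed 0.5% rate, each leading only to a tabulation. If only the combined line is allowed to prompt, the figure is 1.9%.
- With 0.005 × 2,300 = 11.5 expected events per arm, the design effect will be poorly estimated.
- The prompt should stay out of the quarterly comparisons in 7.1. Over four looks under no effect, adding even the combined line alone raises false upward prompts from 0.5% to 4.1%.

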9.4.5 BASELINE DESCRIPTIVE STATISTICS

The cluster-randomized design of the trial increases the probability of study arm imbalance on patient factors. Baseline patient factors will be summarized and compared across the three study arms using descriptive statistics (mean, SD, median, interquartile range, proportion) and confidence intervals. Results of statistical tests conducted on patient factors by study arm will not be used to inform covariate adjustment. Rather, in a-priori sensitivity analyses the models described in the analysis plan will include patient covariates of age, race, and public pay status.

9.4.6 PLANNED INTERIM ANALYSES

There is no interim analysis planned for ending the study due to futility or efficacy.

9.4.7 SUB-GROUP ANALYSES

Not applicable

9.4.8 TABULATION OF INDIVIDUAL PARTICIPANT DATA

Not applicable

9.4.9 EXPLORATORY ANALYSES

Not applicable

10 SUPPORTING DOCUMENTATION AND OPERATIONAL CONSIDERATIONS

10.1 REGULATORY, ETHICAL, AND STUDY OVERSIGHT CONSIDERATIONS

10.1.1 INFORMED CONSENT PROCESS

10.1.1.1 CONSENT/ASSENT AND OTHER INFORMATIONAL DOCUMENTS PROVIDED TO PARTICIPANTS

The following consent materials will be submitted with the IRB application: a phone script describing the study intervention, study procedures, and risks are given to the participant for verbal consent (patient participant survey call).

Refer to the *Schedule of Activities* for clarity about timing and study population.

10.1.1.2 CONSENT PROCEDURES AND DOCUMENTATION

Informed consent is a process that is initiated prior to the individual's agreeing to participate in and answer questions as part of the patient survey. Using an IRB-approved script, CESR staff will explain the research study to the participant and answer any questions that arise. A verbal explanation will be provided in terms suited to the participant's comprehension of the purposes, procedures, and potential risks of the study and of their rights as research participants. Participants will be informed that participation is voluntary and that they may withdraw from the study at any time. The rights and welfare of the participants will be protected by emphasizing to them that the quality of their medical care will not be affected if they decline to participate in this study.

In addition to completion of training in practices of standardized telephone-administered survey research, CESR staff are trained in HIPAA and the responsible conduct of research through CITI.

10.1.2 STUDY DISCONTINUATION AND CLOSURE

This study may be temporarily suspended or prematurely terminated if there is sufficient reasonable cause. If the study is prematurely terminated or suspended, the PIs will promptly inform study participants, the IRB, and NIDCR and will provide written notification, including the reason(s) for the termination or suspension. Study participants will be contacted, as applicable, and be informed of changes to study visit schedule.

Circumstances that may warrant termination or suspension include, but are not limited to:

- Determination of unexpected, significant, or unacceptable risk to participants
- Demonstration of efficacy that would warrant stopping
- Insufficient compliance to protocol requirements
- Data that are not sufficiently complete
- Determination that the primary endpoint has been met
- Determination of futility

Study may resume once concerns about safety, protocol compliance, and data quality are addressed, and satisfy the PIs, IRB and/or NIDCR.

10.1.3 CONFIDENTIALITY AND PRIVACY

Participant confidentiality and privacy is strictly held in trust by the participating investigators and their staff. This confidentiality is extended to the clinical information relating to participants. Therefore, the study protocol, documentation, data, and all other information generated will be held in strict confidence. No information concerning the study or the data will be released to any unauthorized third party without prior written approval of the PIs.

All research activities will be conducted in as private a setting as possible.

The Data and Safety Monitoring Board, representatives of HealthPartners IRB, and/or regulatory agencies may inspect all documents and records required to be maintained by the investigator, including but not limited to, medical records (office, clinic, or hospital) and pharmacy records for the participants in this study. The clinical study site will permit access to such records, as required.

The study participant's contact information will be securely stored at each clinical site for internal use during the study. At the end of the study, all records will continue to be kept in a secure location for as long a period as dictated by the reviewing IRB, Institutional policies, or NIDCR requirements.

Study participant research data, which is for purposes of statistical analysis and scientific reporting, will be transmitted to and stored at HealthPartners Institute. This will not include the participant's contact or identifying information. Rather, individual participants and their research data will be identified by a unique study identification number. The study data entry and study management systems used by clinical sites and by HealthPartners research staff will be secured and password protected. At the end of the study, all study databases will be de-identified and archived at the HealthPartners Institute.

To further protect the privacy of study participants, a Certificate of Confidentiality will be issued by the NIH. This certificate protects identifiable research information from forced disclosure. It allows the investigator and others who have access to research records to refuse to disclose identifying information on research participation in any civil, criminal, administrative, legislative, or other proceeding, whether at the federal, state, or local level. By protecting researchers and institutions from being compelled to disclose information that would identify research participants, Certificates of Confidentiality help achieve the research objectives and promote participation in studies by helping assure confidentiality and privacy to participants.

